## 1. SYNOPSIS

#### Title:

A Randomized, Double-Blind, Vehicle-Controlled, Parallel Group Study of the Dose-Response Profile of A-101 Topical Solution in Subjects with Seborrheic Keratosis of the face.

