## **Objectives:**

The main objective of this study is to evaluate the dose-response relationship of two concentrations of hydrogen peroxide (A-101) solution (32.5% and 40%) when applied to individual seborrheic keratosis (SK) lesions (target lesions) on the face compared with a matching A-101 Solution Vehicle.

Each subject will have one target lesion on the face.

A further objective is to evaluate the safety and efficacy of two concentrations of A-101 solution and its matching vehicle when applied to SK target lesions on the face.

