# 3. STUDY OBJECTIVES

The main objective of this study is to evaluate the dose-response relationship of 2 concentrations of A-101 Solution and its matching A-101 Solution Vehicle when applied to SK target lesions on the face. A further objective is to evaluate the safety and efficacy of 2 concentrations of A-101 Solution and its matching A-101 Solution Vehicle when applied topically up to 2 times to SK target lesions on the face.

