# 9. STATISTICAL ANALYSES

## 9.1. Statistical Analysis of Clinical Indices

The primary effectiveness analysis will consist of mean change from baseline to Visit 8 PLA performed using Analysis of Covariance (ANCOVA) with baseline PLA as the covariate. The analysis will be performed at each post-baseline visit with emphasis on Visit 8. Comparisons between vehicle and each active treatment group will be performed within the model using least-squares means and the common error term. The primary efficacy analyses will be based on the per protocol (PP) population, defined as all randomized subjects who completed the study with no major protocol violation.

A secondary efficacy analysis of a separate comparison between each active treatment group and the vehicle treatment group based on the proportion of subjects whose target lesion is judged to be clear on the PLA (PLA = 0) at Visit 8. A separate Cochran-Mantel-Haenszel (CMH) test stratified by Site will be used for each comparison. A secondary efficacy analysis will also be conducted using this same methodology, but based on SSA.

Secondary analyses will initially be performed on the PP population, but will also be performed on the intent-to-treat (ITT) population defined as all randomized subjects with non-missing data at baseline and at least one post-baseline visit. As a secondary analysis, the primary efficacy analysis will be performed using the ITT population. For all ITT-population analyses, missing efficacy data will be imputed from the last non-missing post-baseline visit carried forward to subsequent missing visits (LOCF).

For all analyses, two-tail alpha will be set to 0.05 with no adjustment for multiple comparisons. ANCOVAs will include Site in the model if doing so improves the sensitivity of the model for comparing treatment groups. As a sensitivity analysis, the primary efficacy analysis will also be run including Site and the Treatment-by-Site interaction. If the interaction term is associated with p < 0.10 then treatment group means for each Site will be examined individually to understand potential site differences. Sites with less than two completed blocks of subjects will be pooled with other such Sites to achieve new pooled analysis Sites that meet this criterion. Sites will

first be ranked by sample size and then pooled in that order until each new pooled analysis Site meets the two-block threshold.

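### Dose-response is the main objective, but Section 9.1 prespecifies no contrast or confidence interval between the 40% and 32.5% solutions

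*Combined protocol and SAP*

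**What the plan says.** The title calls the trial a "Study of the Dose-Response Profile of A-101 Topical Solution in Subjects with Seborrheic Keratosis of the face". The synopsis objective begins "The main objective of this study is to evaluate the dose-response relationship of two concentrations of hydrogen peroxide (A-101) solution" and ends "on the face compared with a matching A-101 Solution Vehicle". Section 3 repeats it: "The main objective of this study is to evaluate the dose-response relationship of 2 concentrations of A-101 Solution", again with the matching vehicle. Both places list safety and efficacy separately, as a further objective.

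Section 9.1 contains all the planned efficacy inference:

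- Primary: ANCOVA on change in PLA to Visit 8 with baseline PLA as covariate. "Comparisons between vehicle and each active treatment group will be performed within the model using least-squares means and the common error term".
- PLA=0 at Visit 8: "A secondary efficacy analysis of a separate comparison between each active treatment group and the vehicle treatment group". "A separate Cochran-Mantel-Haenszel (CMH) test stratified by Site will be used for each comparison".
- SSA: "A secondary efficacy analysis will also be conducted using this same methodology, but based on SSA".

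Alpha is two-sided 0.05, without adjustment for multiple comparisons. Section 9.3 sizes the study on the highest dose against vehicle and gives no expected rate for 32.5%. Sections 9.1 to 9.3 contain no contrast between the two active arms, no trend test, no dose-response model and no confidence interval for any comparison.

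**The concern.** A dose-response question with two active levels and vehicle has two parts: whether each dose beats vehicle, and how much the response changes from 32.5% to 40%. The planned comparisons cover the first part. For the second, the report will contain per-arm results and two p-values against vehicle. If one p-value falls below 0.05 and the other does not, it is natural to read a dose difference into the split, although the difference between a significant and a non-significant result need not itself be significant. An analyst who then adds the missing contrast after unblinding must choose its endpoint, population and error term with the data in view. The default, the common error term named in Section 9.1, suits this contrast poorly, as shown in the working.

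**Working it through.** **Inputs.** From Section 9.3: 32 completers per arm, clear rate 0.325 at the highest dose and 0.031 on vehicle, two-sided alpha 0.05, power about 87%, and power above 90% for the ANCOVA. From the synopsis: about 108 subjects at about 36 per center, so 108/36 = 3 Sites. Not given, and therefore assumed: the 32.5% clear rate, the SD of PLA change, the baseline PLA mix and the partial-response rates.

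**1. The plan's own figure.** Pooled z test: mean rate (0.325 + 0.031)/2 = 0.178. Null SE = √(2 × 0.178 × 0.822/32) = 0.0956. Alternative SE = √((0.325 × 0.675 + 0.031 × 0.969)/32) = 0.0883. Power = Φ((0.294 − 1.96 × 0.0956)/0.0883) = Φ(1.207) = 88.6%. Fisher's exact test gives 85.2%. The stated 87% reproduces, but it concerns 40% against vehicle only.

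**2. How often the vehicle tests split when the doses are equal.** Set both doses to 0.325 and use the uncorrected chi-square test. Let v be the number of clear vehicle subjects and π(v) the chance that a dose arm is then significant. P(exactly one significant) = Σ P(v) × 2π(v)(1 − π(v)).

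| v | P(v) | clear subjects needed in a dose arm | π(v) | contribution |
|---|---|---|---|---|
| 0 | 0.365 | 4 | 0.998 | 0.002 |
| 1 | 0.374 | 6 | 0.973 | 0.020 |
| 2 | 0.185 | 8 | 0.864 | 0.043 |
| 3 | 0.059 | 10 | 0.625 | 0.028 |
| 4 | 0.014 | 11 | 0.476 | 0.007 |

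With the remaining values of v, the total is 10.1%. Simulation (200,000 runs) gives 10.0% unstratified and 10.6% with CMH over 3 Sites. In the split trials the Newcombe interval for 40% minus 32.5% includes zero in about 80% (81% when Site-stratified), so it wrongly excludes zero in about 20%.

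**3. The same on the ANCOVA.** I simulated 20,000 trials per setting with equal doses, the clear rates above, and assumed shares of uncleared lesions improving one grade. With half the lesions at baseline PLA 3:

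| improving (active, vehicle) | power vs vehicle | exactly one dose significant |
|---|---|---|
| 0.2, 0.1 | 90.1% | 16.2% |
| 0.3, 0.1 | 95.3% | 8.2% |
| 0.4, 0.1 | 98.1% | 3.4% |
| 0.6, 0.1 (shorter run) | about 99.8% | about 0.3% to 0.4% |

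For settings with about 90% to 98% power, the between-dose interval with HC3 (heteroscedasticity-robust) standard errors includes zero in about 72% to 83% of the split trials, and so wrongly excludes it in about 17% to 28%.

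**4. Why the error term matters.** A vehicle arm that rarely responds varies less than the active arms, and pooling it in shrinks the error for a contrast that does not involve it. The clear/not-clear indicator shows the size of the effect. The active variance is 0.325 × 0.675 = 0.219 and the vehicle variance 0.031 × 0.969 = 0.030. The pooled variance is (2 × 0.219 + 0.030)/3 = 0.156. The SE ratio is √(0.156/0.219) = 0.844, so a nominal 5% test becomes 2 × (1 − Φ(1.96 × 0.844)) = 9.8%. In the PLA-change simulations the common error term gave 8.4% to 9.9% between-dose false positives; HC3 gave 4.4% to 5.1%.

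**5. Precision of the added intervals, 32 per arm.** Clear rate, Site-stratified Newcombe, 40% at 0.325:

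| assumed 32.5% rate | half-width | excludes zero |
|---|---|---|
| 0.10 | 0.195 | 58% |
| 0.20 | 0.207 | 20% |
| 0.25 | 0.212 | 10% |
| 0.325 | 0.218 | 5% |

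On PLA change, the mean HC3 half-width is 0.51 to 0.64 grades over the assumed scenarios with power of about 90% to 98%.

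**The case against.** The strongest reply is that the objective is largely met. The synopsis frames dose-response against vehicle, and testing each dose against vehicle is a recognised reading of that. The three-arm ANCOVA supplies a least-squares mean per arm, so the dose step is a subtraction away. Section 9.1 plans no interval for any comparison, so the omission is not peculiar to this one. Much of this stands. A reader might infer that the main objective has no analysis, or that the dose difference cannot be estimated. The documents support neither: the vehicle part is answered, and the point difference can be derived. What is missing is a prespecified contrast and its uncertainty.

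A reader might also infer that the sponsor intends to rank the doses by significance, or that the sample size is wrong. No section says the first, and the stated power reproduces.

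It is also fair to say that the remedy is imperfect. In the trials it targets, the interval still points to a false difference in about 17% to 28%. With a true difference of 0.325 against 0.20 it excludes zero only 20% of the time. It will often be inconclusive. The ANCOVA split rate depends on the assumed power and almost vanishes when power is very high. These points limit the benefit. They do not remove the case for stating in advance how the two doses will be compared, particularly as the obvious unplanned contrast would be miscalibrated under these assumptions.

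**Conclusion.** The concern holds as a prespecification gap. Dose-response is the main objective, but the only planned inference about the two doses is whether each differs from vehicle. With equal doses, a misleading split occurs in about 10% of trials on PLA=0. On the ANCOVA it occurs in about 16% at 90% power, 3% at 98% and below 1% at higher power. A planned between-dose interval would include zero in roughly 70% to 80% of the splits, except at the very highest power, where they are too rare to matter. The text of the gap is certain. The sizes rest on an assumed 32.5% rate equal to 0.325 and on assumed partial-response rates and baseline mix. The vehicle comparisons and the 87% power calculation stand. Label: cheap improvement.

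**What to change.** In Section 9.1, prespecify for Visit 8, in the PP population and repeated in ITT, as estimation only:

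1. The 40%-minus-32.5% least-squares-mean difference in PLA change from the same ANCOVA, with a 95% CI from robust (HC3) or arm-specific standard errors.
2. The 40%-minus-32.5% difference in the proportion with PLA=0, and likewise SSA=0, each with a 95% CI for a difference in proportions, for example Newcombe stratified by the (pooled) Sites used for the CMH tests.

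State that the 87% power does not apply to these estimates. State that the intervals will be wide: about ±20 to 22 points on clear rate and, under the assumed scenarios, about ±0.5 to 0.65 PLA grades with HC3. Add that an interval including zero does not show the doses to be equal, and that the doses will not be ranked by which one reached p<0.05 against vehicle. Leave the vehicle comparisons as written.

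The cost is a few lines of text and one extra table, with no new data or subjects. The ANCOVA table will carry two kinds of standard error, which needs a footnote, and the between-dose result may be inconclusive.

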# 4.5.3. Prohibited therapies

During the course of this study, subjects are prohibited from using therapies listed in the exclusion criteria (Section 4.4). The investigator should notify the Aclaris Therapeutics, Inc. Medical Monitor (Section 7.2) immediately if any prohibited therapies are required to ensure subject safety.

Starting with Visit 2, subjects must:

- On study visit days, not apply any topical products (*e.g.*, moisturizers, makeup, sunscreens, etc.) to the target lesion within 12 hours prior to any study visit (Note: routine cleansing products are allowed)
- Not apply any topical products to the target lesion for at least 6 hours after any study medication application.

Starting 6 days prior to Visit 2, and for the remainder of the study, subjects must not use any peroxide containing products on her/his face or head.

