## 4.6. Subject Discontinuation from the Study

Subjects will be informed that they are free to withdraw from the study at any time and for any reason.

The investigator may remove a subject from the study if, in the investigator's opinion, it is not in the best interest of the subject to continue the study. Examples of other reasons subjects may be discontinued from the study are a change in compliance with an inclusion or exclusion criterion, occurrence of AEs, occurrence of pregnancy or use of a prohibited therapy. Immediately (within 24 hours) notify the Aclaris Therapeutics, Inc. study monitor of discontinuation.

In case of premature discontinuation of study participation, efforts will be made to perform all final study day assessments. The date the subject is withdrawn from the study and the reason for discontinuation will be recorded on the subject's case report forms (CRFs). All withdrawn subjects with ongoing AEs will be followed as appropriate (Section 7.2.1).

The study may be discontinued at the discretion of Aclaris Therapeutics, Inc. Some examples of reasons for discontinuation are the occurrence of the following:

- Increased frequency, severity or duration of known AEs
- Medical, regulatory or ethical reasons affecting the continued performance of the study
- Difficulties in the recruitment of subjects.

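### The primary active-versus-vehicle ANCOVA uses the per-protocol set; the all-randomized analysis should be primary and per-protocol supportive

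*Combined protocol and SAP*

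**What the plan says.** Section 9.1 tests change from baseline to Visit 8 PLA by ANCOVA with baseline PLA as covariate, comparing each active arm with vehicle. On the population it says: "The primary efficacy analyses will be based on the per protocol (PP) population, defined as all randomized subjects who completed the study". The full condition is that they "completed the study with no major protocol violation". The supplied text does not define a major violation and gives no reason for putting per-protocol (PP) first.

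The alternative is planned but ranked lower: "As a secondary analysis, the primary efficacy analysis will be performed using the ITT population". That set is the "intent-to-treat (ITT) population defined as all randomized subjects with non-missing data at baseline and at least one post-baseline visit". Missing ITT values are filled by LOCF from post-baseline visits, and no other missing-data method is given.

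Several sections bear on who stays in PP:

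- Section 4.6 lists among reasons for discontinuation "occurrence of AEs, occurrence of pregnancy or use of a prohibited therapy". For early exits it adds that "efforts will be made to perform all final study day assessments".
- Section 4.5.3: "During the course of this study, subjects are prohibited from using therapies listed in the exclusion criteria". The Section 4.4 list includes topical glucocorticosteroids and antibiotics on or near the target lesion where the investigator judges that they interfere.
- Section 7.1.1 foresees therapy to manage a worsened target-lesion assessment.
- Section 5.10.2 discharges any subject whose blind is broken, and requires the blind to be broken after eyewash use.
- Section 5.7.8 does not require removal solely for refusing retreatment.
- Section 10.3 has evaluability decided before database lock, but does not say before unblinding.

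Section 9.3 defines its 32 subjects per arm on the PP set. Section 4.1 randomizes about 36 per arm, the Synopsis aims for 96 completers of 108, and Section 4.8 rules out replacement.

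**The concern.** Completing the study and avoiding a major violation are both outcomes of the trial. A local reaction that needs a prohibited topical product, an adverse event that leads to withdrawal, or an eye exposure that leads to unblinding can each take a subject out of PP. The first two could plausibly differ between 32.5% or 40% peroxide and vehicle. Unblinding can occur in any arm.

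The primary estimate and p-value are then valid only if the subjects left in PP remain comparable across arms, which randomization no longer guarantees. If exclusion is related to outcome and differs by arm, the result can err for or against A-101.

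The planned ITT analysis is better protected but does not include everyone randomized. The first scheduled post-baseline PLA is Visit 4, Day 22 (Section 6.1.2). A subject who leaves before then has nothing to carry forward unless an exit PLA is obtained.

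**Working it through.** **1. Planned loss.** From the Synopsis and Section 4.1: 1 − 96/108 = 12/108 = 11.1%, and 32/(1 − 12/108) = 36 per arm, which matches the plan.

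**2. The plan's own power figure.** Section 9.3 gives n = 32, p₁ = 0.325, p₂ = 1/32 = 0.03125, two-sided alpha 0.05 and about 87% power. It names no method, so two normal formulas are shown. With d = 0.29375 and mean proportion 0.178125:

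- s₀ = √(2 × 0.178125 × 0.821875/32) = 0.0957
- s₁ = √((0.325 × 0.675 + 0.03125 × 0.96875)/32) = 0.0883
- Pooled variance: Φ(d/s₀ − 1.96) = 86.7%
- Pooled null, unpooled alternative: Φ((d − 1.96 s₀)/s₁) = 88.6%

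Fisher's exact test gives about 85%. The stated 87% reproduces. The figure above 90% for the ANCOVA cannot be checked, because no mean change or SD is given.

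**3. Simple bound on the bias.** Suppose k of 36 active subjects leave, all of them non-improvers, and vehicle loses none. PP then overstates mean improvement in that arm by k/(36 − k): 4/32 = 12.5%, 5/31 = 16.1%, 6/30 = 20.0%.

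**4. Null simulation (illustrative).** There were 20,000 runs per scenario (Monte Carlo error about 0.15 to 0.25 points), 36 per arm, and the same outcome law in all three arms. The three-arm ANCOVA used baseline PLA and a common error term. These inputs are assumed, apart from the 3.1% vehicle clear rate from Section 9.3:

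- Baseline PLA is 2 or 3 with equal probability.
- Three Visit 8 laws (clear / one grade better / unchanged): 3.1/30/66.9%, 7/33/60% and 3.1/45/51.9%.
- Visit 4 PLA equals the Visit 8 grade with probability 0.5, otherwise baseline.
- Half of leavers go before Visit 4.
- Losses per active arm/vehicle are 4/4, 5/2 or 6/0, and vehicle losses are random.
- Every PP exclusion is treated as loss.

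Two-sided type I error, 40% versus vehicle, range over the three laws and, unless shown, over the three loss splits:

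| Who leaves the active arms | PP | ITT/LOCF |
|---|---|---|
| Random | 4.6–5.2% | 4.6–5.1% |
| Non-improvers four times as likely | 5.4–7.1% | 4.9–5.5% |
| Only non-improvers | 6.2–8.1% (4/4); 7.0–9.6% (5/2); 8.2–12.1% (6/0) | 5.6–7.2% |
| Improvers four times as likely | 6.3–8.4% | 5.7–8.2% |
| Only improvers | 8.7–25.7% | 7.3–19.0% |

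In the last two rows most PP rejections go against A-101. False wins for active are only 0.9–1.5% and 0.3–0.9%, against a nominal 2.5%. With a Visit 8 PLA for every randomized subject, the error was 4.7–5.3% throughout.

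A separate normal-approximation check assumed SD 1.0 and exclusions from one active arm only, with the excluded subjects 0.5 to 1.5 grades worse than those retained. The bias is (grade gap × k)/36. For k = 4 it is 0.06 to 0.17 grade, and the error is 5.6 to 10.5%.

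**5. Power for PLA = 0 on 36 randomized per arm, missing counted as not clear.** Active rate = 0.325 × completers/36; vehicle rate = 0.03125 × completers/36.

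| Losses (active/vehicle) | Rates | Pooled | Pooled null, unpooled alternative |
|---|---|---|---|
| 4/4 | 0.2889 vs 0.0278 | 85.9% | 87.5% |
| 5/2 | 0.2799 vs 0.0295 | 83.6% | 85.1% |
| 6/0 | 0.2708 vs 0.0313 | 81.0% | 82.4% |

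**The case against.** The main objective is dose-response in about 108 subjects, with no multiplicity adjustment, so this does not read as a confirmatory trial. The ITT version of the primary ANCOVA is already promised, so no result would be hidden and the core change is one of labels.

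The more plausible scenarios give modest inflation. The 8.2 to 12.1% needs every active leaver to be a non-improver with no loss on vehicle, a pattern that nothing in the documents suggests. The route from treatment to exclusion is permissive: Section 4.6 allows discontinuation without requiring it, and no section says that prohibited therapy is a major violation. Treatment is at most two staff-applied applications, and refusing the second does not require removal. Section 5.7.3 restricts access to the randomization list, which lessens the worry about unblinded selection.

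LOCF does not restore nominal error when improvers leave, and there it does little better than PP. Counting a missing PLA as not clear is also an assumption, and its error rate was not simulated.

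Most of this stands, but it bears on weight. It supports calling the inflation modest and the direction unknown, and it shows that promoting the ITT/LOCF analysis unchanged is not enough. It gives no reason to prefer PP for a comparison of active with vehicle.

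**Conclusion.** The concern holds and should be fixed. The primary comparison rests on a set defined by post-randomization events that treatment can affect, while the better protected analysis is secondary and itself omits subjects with no post-baseline data.

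The principle is firm; the size is not. Inflation is absent under random loss and about 0.4 to 2.1 points (5.4 to 7.1% against 5%) under a fourfold tilt towards non-improvers. Larger figures need extreme patterns. All of these rest on assumed outcome laws, loss splits and timing. The documents do not show that material bias will occur, or in which direction.

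**What to change.** In Section 9.1 and the Synopsis:

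- Make all randomized subjects, analysed as randomized, the primary population, with PP supportive.
- Use the exit PLA that Section 4.6 already seeks, and the Visit 8 PLA of subjects excluded from PP only for a violation. The latter need no imputation.
- State how subjects with no post-baseline PLA are included, for example by multiple imputation from baseline PLA. Carrying baseline forward as no change is not proposed as a better rule: it gave 5.4 to 12.4% error under the fourfold improver tilt, where ITT/LOCF gave 5.7 to 8.2%.
- LOCF may stay, but add at least one sensitivity analysis under a different assumption, such as a repeated-measures model on Visits 4, 6, 7 and 8 or multiple imputation.
- For PLA = 0, count a missing Visit 8 PLA as not clear, check this with another assumption, and restate the Section 9.3 power on 36 randomized per arm.
- For the supportive PP set, list what counts as a major violation and state that membership is fixed before unblinding.

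The cost is wording, routine programming and a slightly lower stated power for PLA = 0: about 86 to 88% with four losses per arm, against 87 to 89% on 32 completers by the same formulas, and about 81 to 82% with six active and no vehicle losses. ANCOVA power cannot be restated until the sponsor supplies a mean PLA change and SD.

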Numerous treatment options exist, and include a plethora of destructive/ablative modalities such as liquid nitrogen cryotherapy, electrodesiccation, lasers of various wavelengths (ablative and non-ablative), radio-frequency ablation, and surgical removal by curettage or surgical excision. There is, however, a notable lack of wellcontrolled clinical trials comparing the efficacy, complications and complication rates of these treatments. There is great variability among practitioners in the methods employed using each of these techniques (e.g., variability in contact time and method of freezing the lesions with liquid nitrogen) with great variability of the results. None of these treatments is, in fact, approved by the Food and Drug Administration (FDA) for the treatment of seborrheic keratosis. While these methods can be effective, many require specialized training and/or the use of expensive equipment, they are painful and may require anesthesia and/or analgesia, and they are often complicated by significant adverse outcomes. Both hypopigmentation and hyperpigmentation, which may be transient, but are often permanent, are common, as is scarring at the treatment site, and the typical post-surgical risks of bleeding and infection increase the risk that the result of the treatment of these lesions may be worse than the disease itself.

Hydrogen peroxide (H2O2) is a compound that is ubiquitous in the environment. It is the simplest peroxide and a potent oxidizing agent commonly used in innumerable household goods including chlorine-free bleaches, general-purpose cleaning products, and disinfectants. Additionally, H2O2 has been employed as the oxidizing component in hair dyes, and has been used in oral hygiene products and tooth-whitening systems for many years. In industry, it is employed in the treatment of wastewater. In high concentrations, it is used in bleaching paper, pulp, and textiles. Clinically, in addition to its use as an oral topical agent noted above, H2O2 is widely employed at low concentrations (*e.g.*, 3%-6%) as a wound irrigant and topical antiseptic/disinfectant, and has been in use medicinally since its introduction into clinical practice by Richardson in 1858.

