## 4.4. Exclusion Criteria

Any subject who meets one or more of the following criteria will not be included in this study:

- 1. Subject has clinically atypical and/or rapidly growing seborrheic keratosis lesions
- 2. Subject has presence of multiple eruptive seborrheic keratosis lesions (Sign of Lesser-Trelat)
- 3. Subject has a current systemic malignancy
- 4. Subject has a history of keloid formation or hypertrophic scarring
- 5. Subject has used any of the following systemic therapies within the specified period prior to Visit 1:
  - Retinoids; 180 days
  - Glucocortico-steroids; 28 days
  - Anti-metabolites (*e.g.*, methotrexate); 28 days
- 6. Subject has used any of the following topical therapies within the specified period prior to Visit 1 on, or in a proximity to the target lesion, which in the investigator's opinion, interferes with the application of the study medication or the study assessments:
  - LASER, light (*e.g.*, intense pulsed light [IPL], photo-dynamic therapy [PDT]) or other energy based therapy; 180 days
  - Retinoids; 28 days
  - Liquid nitrogen, electrodesiccation, curettage, imiquimod, 5flurouracil, or ingenol mebutate; 60 days
  - Glucocortico-steroids or antibiotics; 14 days
- 7. Subject currently has or has had any of the following within the specified period prior to Visit 1 on, or in a proximity to the target lesion, which in the investigator's opinion, interferes with the application of the study medication or the study assessments :
  - A cutaneous malignancy; 180 days
  - Experienced a sunburn; 28 days
  - A pre-malignancy (*e.g.*, actinic keratosis); currently
  - Body art (e.g., tattoos, piercing, etc.); currently
  - Excessive tan; currently
- 8. Subject has a history of sensitivity to any of the ingredients in the study medications
- 9. Subject has any current skin disease (*e.g.*, psoriasis, atopic dermatitis, eczema, sun damage, etc.), or condition (*e.g.*, sunburn, excessive hair, open wounds) which, in the investigator's opinion, might put the subject at undue risk by study participation or interfere with the study conduct or evaluations

10. Subject has participated in an investigational drug trial in which administration of an investigational study medication occurred within 30 days prior to Visit 1.

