# 6.1.2. Physician's Lesion Assessment (PLA)

The PLA is the investigator's assessment of the average overall severity of the target lesion at a particular time point. The investigator should NOT refer to any other assessments to assist with these assessments.

At Visits 1, 2, 4, 6, 7 and 8, the investigator will assess the target lesion using the scale below and report the one integer that best describes the average overall severity of the target lesion. At Visit 2, and if appropriate Visit 4, the investigator must complete the PLA prior to the study medication application.

| Physician's Lesion Assessment |   |  |  |
|-------------------------------|---|--|--|
| Grade                         | Descriptor  |  |  |
| 0                             | Clear: no visible seborrheic keratosis lesion                               |  |  |
| 1                             | Near Clear: a visible seborrheic keratosis lesion with a surface appearance |  |  |
|                               | different from the surrounding skin (not elevated)                          |  |  |
| 2                             | Thin: a visible seborrheic keratosis lesion (thickness ≤1mm)                |  |  |
| 3                             | Thick: a visible seborrheic keratosis lesion (thickness >1mm)               |  |  |

At Visit 1 for the subject to be enrolled and at Visit 2 for the subject to be randomized the target lesion must have a PLA grade  $\geq$  2.

At Visits 2 and 8, the subject must complete the SSA (Section 6.1.1) assessment prior to the investigator performing the PLA.

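### A target lesion removed by a non-study procedure can enter the ITT clearance analyses as clear, because Section 9.1 has no rule for it; the per-protocol primary analysis is exposed only in a narrow case.

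*Combined protocol and SAP*

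**What the plan says.** **Scoring.** PLA grade 0 is "Clear: no visible seborrheic keratosis lesion" (Section 6.1.2). Grade 0 on the SSA is likewise defined by the absence of a visible lesion (Section 6.1.1). Both describe the lesion at one time point, and neither asks how it disappeared.

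**Discontinuation.** Section 4.6 gives use of a prohibited therapy as an example of why a subject may be discontinued, so it is not mandatory. It adds: "In case of premature discontinuation of study participation, efforts will be made to perform all final study day assessments".

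**Populations and missing data (Section 9.1).** The primary analysis uses the per-protocol (PP) population, "defined as all randomized subjects who completed the study with no major protocol violation"; a major violation is not defined. The ITT population is "defined as all randomized subjects with non-missing data at baseline and at least one post-baseline visit". For ITT analyses only, "missing efficacy data will be imputed from the last non-missing post-baseline visit carried forward to subsequent missing visits (LOCF").

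**Procedures.** Under Section 4.5.3, "subjects are prohibited from using therapies listed in the exclusion criteria". Section 4.4 covers laser, light and other energy-based therapy and, in another item, "Liquid nitrogen, electrodesiccation, curettage, imiquimod" and further topical agents. It does not name excision, shave removal or biopsy. Section 2.1 does list "surgical removal by curettage or surgical excision" among the treatments in use for seborrheic keratosis (SK), and says removal may be indicated where histology is wanted.

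**The concern.** Take a subject whose facial target lesion is removed elsewhere between Visits 6 and 8. The lesion is gone at the next assessment, and by the grade definitions the PLA and SSA are 0. The procedure, not the study medication, produced that grade, yet the ITT clearance analyses would count it as a success.

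The event is plausible. Section 2.1 describes the face as cosmetically sensitive and lists many alternative treatments, a third of subjects receive vehicle, and 84 days of untreated follow-up come after Visit 4.

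The direction of bias is not fixed. Removal of persisting vehicle lesions raises the vehicle clearance rate and hides an effect. Removal of residual or irritated active lesions inflates that arm and can distort the dose-response comparison, the main objective. Section 9.3 plans on at most one clear vehicle subject in 32, so a very small number of such cases matters.

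**Working it through.** **1. Trace the case through the rules.**

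| Path after removal | ITT | PP |
|---|---|---|
| Stays in, attends Visit 8 | Observed PLA 0 and SSA 0: clear | In, as PLA 0, unless judged a major violator |
| Discontinued, final assessment done after removal | 0 carried to Visit 8 if that assessment counts as a post-baseline visit, which is not stated | Out: not a completer |
| Discontinued, nothing assessed after removal | Earlier post-baseline PLA grade carried | Out: not a completer |

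LOCF therefore creates a false clearance in one path only, and never in PP. In PP the open case is an observed 0 in a completer. Excision, shave removal and biopsy are the main examples because Section 4.4 does not list them. Listed procedures can be excluded as violations, though Section 9.1 does not say that they will be.

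**2. Reproduce the plan's power.** Inputs from Section 9.3: n = 32 completers per arm, active 0.325, vehicle 0.031, two-sided alpha 0.05, stated power about 87%.

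Normal approximation: power = Φ{[pA − pV − 1.96·√(2p̄(1−p̄)/n)] / √(pA(1−pA)/n + pV(1−pV)/n)}, with p̄ = (0.325 + 0.031)/2 = 0.178.

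- 1.96·√(2 × 0.178 × 0.822/32) = 0.187
- √((0.2194 + 0.0300)/32) = 0.0883
- Φ[(0.294 − 0.187)/0.0883] = Φ(1.21) = 88.6%

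Exact power of Fisher's test is 85.2%. The stated 87% lies between the two. With 12/108 = 11.1% dropout, 32/(1 − 1/9) = 36 randomized per arm, as planned.

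**3. Add false vehicle clearances.** Exact power = Σ over (a, b) of Bin(a; n, 0.325) × Bin(b; n, pV) × [test p ≤ 0.05]. The single-stratum Mantel-Haenszel statistic is (N−1)(an − bn)²/[n²·m(N−m)], with N = 2n and m = a + b. Each assumed removal raises pV by 1/n. At 36 per arm the starting point is 1/36.

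| n per arm | Vehicle rate | Fisher | Mantel-Haenszel |
|---|---|---|---|
| 32 | 1/32 = 0.031 | 85% | 93% |
| 32 | 2/32 = 0.063 | 70% | 80% |
| 32 | 3/32 = 0.094 | 53% | 65% |
| 36 | 1/36 = 0.028 | 92% | 96% |
| 36 | 2/36 = 0.056 | 80% | 88% |

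The ITT exposure is better judged at 36 per arm, since 32 is the PP completer target. The planned test is stratified by site, so the Mantel-Haenszel column is an approximation.

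**4. At fixed counts (Fisher p).** With 10/32 against 1/32 clear, p = 0.006; one false vehicle clearance gives 0.022 and two give 0.060. With 12/36 against 1/36, p = 0.001; three give 0.045 and four give 0.094.

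**5. Direction (normal approximation, n = 32).** If 5% of uncleared vehicle lesions are removed, the vehicle rate is 0.031 + 0.05 × 0.969 = 0.079 and power falls from 88.6% to about 70%. If 5% of uncleared active lesions are removed instead, the active rate is 0.325 + 0.05 × 0.675 = 0.359 and power rises spuriously to about 93%.

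**6. Primary endpoint.** One removed vehicle lesion can move the PP vehicle mean PLA by at most 3/32 = 0.09 grade. The documents give no standard deviation, so this does not convert to power.

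**The case against.** The strongest reply is that silence is being read as a rule. No section says that a removed lesion is scored 0 or that rescue counts as success. The bar in Section 6.1.2 is on consulting other assessments, not on knowing the therapy history, and at Visit 8 therapy changes are queried before the PLA is done (Section 5.3.7). This is fair. But the grade still follows from its definition, and knowing of the procedure gives the investigator no other grade to assign.

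A reader might infer that LOCF puts false clearances into the primary analysis. It does not: LOCF is stated for ITT only, and discontinued subjects leave PP.

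A reader might also infer that an excised subject necessarily stays in PP because excision is unlisted. The documents do not support that. Section 9.1 does not confine violations to the list, Section 4.5.2 asks subjects not to change concomitant therapies and requires new ones to be recorded, Section 4.6 allows discontinuation for a change in compliance with an entry criterion, and Section 10.3 has evaluability determined before database lock. These safeguards narrow the PP exposure. They leave it to judgement, and none of them sets the ITT outcome.

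Finally, the number of removals is assumed, and the power figures concern a secondary endpoint. Both stand.

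**Conclusion.** The point holds as a gap in the ITT rules: read literally, Sections 9.1, 6.1.1, 6.1.2 and 4.6 let a lesion removed by non-study means count as clear on PLA and SSA. The PP primary analysis is exposed only for a completer not judged a major violator. The documents do not support saying that the plan adopts rescue as success, that the primary analysis is generally compromised, or that the bias runs in a known direction.

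On the assumption of one extra vehicle clearance, power for the secondary PLA = 0 comparison drops by 15 points (Fisher) or 13 (Mantel-Haenszel) at 32 per arm, and by 12 or 8 at 36 per arm, from the rounded figures. If no lesion is removed, nothing changes. The plan should settle this before unblinding, because a decision on one or two subjects could decide significance.

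**What to change.** Add to Section 9.1:

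- PLA, SSA and lesion dimensions recorded after any non-study removal, biopsy or destructive treatment of the target lesion are not used as outcome.
- For PLA change and for PLA = 0, use the last PLA before the procedure, or baseline if there is no earlier post-baseline PLA. The first post-baseline PLA is at Visit 4, so earlier removals need that provision. A lesion not clear before the procedure then counts as not clear, and one already at grade 0 keeps that grade.
- For SSA, taken only at Visits 2 and 8, the subject counts as not clear.
- Such a procedure is a major protocol violation for the PP population.

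Record the procedure date on the CRF. Sections 2.1, 4.4 and 4.5.3 must be reconciled on surgical excision; which procedures are prohibited is for the sponsor to decide.

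The cost is a few sentences and one CRF field, since non-drug therapies are already collected under Section 4.5.2. The small downside is that post-procedure assessments go unused.
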